5.1 Schedule of Assessments

The schedule of assessments is presented in table format in the study synopsis

Study Phase	Screening	Treatment														
		1	2	3	4	5	6	7	8	9	10	11	12	13	14	15
VISIT NUMBER	0	1	2	3	4	5	6	7	8	9	10	11	12	13	14	15
WEEK	0	1	2	3	4	5	6	7	8	9	10	11	12	13	14	15
Informed consent	X	X														
Study drug		X	X	X	X	X	X	X	X	X	X	X	X	X	X	X
Study drug Instruction		X														
Medical history ²	X ²	X ²			X ²				X ²				X ²			
Physical examination ³	X ³	X ³			X ³				X ³				X ³			
Adverse Event		X			X				X				X			
Record concomitant medications ⁴	X	X			X				X				X			
Vital signs ⁵	X	X			X				X				X			
CBC w/ differential, platelet count	X	X			X				X				X			
Comprehensive Metabolic Panel (CMP)	X	X			X				X				X			
Urinalysis and Urine protein/creatinine	X	X														
Urine Pregnancy test ⁷	X	X			X				X				X			
HBsAg, HBcAb, HCV**Not required if collected 6 months prior to screening	X															
Serum immunoglobulin levels (IgM, IgE, IgG)	X	X														
Serum IgG subclasses	X	X			X				X				X			
C3 and C4	X															
Mechanistic samples	X	X			X								X			
Fasting lipid profile	X	X			X				X				X			
CT chest, abdomen, pelvis ⁸	X															
IgG4-RD RI	X	X			X				X				X			
Physician Global Activity VAS	X	X			X				X				X			
Symptom Severity Index	X	X			X				X				X			
Glucocorticoid Toxicity Index	X	X			X				X				X			
SF-36 Health Survey	X	X			X				X				X			

Study Phase											
VISIT NUMBER	6				7				8	9	10/EO
WEE	16	17	18	19	20	21	22	23	24	28	36
Informed consent											
Study drug administration	X	X	X	X	X	X	X	X	X		
Medical history ²	X				X ²				X	X ²	X ²
Physical examination ³	X				X ³				X	X ³	X ³
Adverse Event assessment ⁴	X				X				X	X	X
Record concomitant medications ⁴	X				X				X	X	X
Vital signs ⁵	X				X				X	X	X
CBC w/ differential, platelet	X				X				X	X	X
Chemistry Panel	X				X				X	X	X
Urinalysis and Urine protein/creatinine											X
Urine Pregnancy test ⁷	X				X				X	X	X
HBsAg, HBcAb, HCV ^o											
Serum immunoglobulin levels (IgM, IgE, IgG)									X		X
IgG subclasses	X				X				X		X
C3 and C4											X
Fasting lipid profile	X				X				X		X
Mechanistic samples									X		
IgG4-RD RI	X				X				X		X
Physician Global Activity VAS	X				X				X		X
Symptom Severity Index	X				X				X		X
Glucocorticoid Toxicity Index	X				X				X		X
SF-36 Health Survey	X				X				X		X

¹The Screening visit (Visit 1) and the Treatment Week 1 (Visit 2) visit could potentially be on the same day

² Includes prior history and treatment of IgG4-RD

³ Complete physical examinations will be performed at Screening, on Day 1 (could potentially be the same visit) and at EOS. Abbreviated, symptom directed PE will be performed at all other visits. Include height at screening only and weight at visits 1, 2, 4, 8, 12, 16, 20, 24, 28, and EOS.

⁴ Adverse events and concomitant medications to be collected by site personnel via phone or email.

⁵ Supine blood pressure and heart rate, body temperature, respiratory rate. Vital sign assessments will be made immediately prior to injection.

⁶ Urinalysis and urine protein/creatinine ratios, at screening or baseline and EOS, and at each study visit if renal involvement

⁷ Pregnancy test only for women of child-bearing potential (urine)

⁷ If the patient has a documented negative result within 60 days before the first dose of abatacept, this item may be omitted

⁸ All patients will need to have a screening CT chest, abdomen and pelvis with head and/or orbits if there is head and neck or extraocular muscle involvement. If abnormal, it will be repeated at approximately 6 months or earlier based on disease activity.

*Not required if collected 6 months prior to screening visit

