5 INVESTIGATIONAL PLAN

Overall Study Design and Plan

Description

This is a Phase 2, prospective, open-label, single center clinical trial in subjects with active IgG4-RD. Approximately 10 subjects with active IgG4-RD will be enrolled. After screening and enrollment, eligible subjects will receive an initial subcutaneous dose of abatacept (125mg) followed by weekly subcutaneous doses of abatacept (125mg) for a total of up to 24 doses (24 weeks). Subjects will be followed on study for 12 weeks following the last dose for a total study period of up to 36 weeks.

After obtaining informed consent, all screening procedures and tests establishing eligibility will be performed on the initial screening visit. Subjects determined to be eligible at screening will receive an initial subcutaneous dose of abatacept (125mg), which will be continued weekly for a total of up to 24 doses (24 weeks). Steroid therapy must be tapered off and discontinued over a 4 week period (taper must be completed no later than week 4). Should patients be deemed to have worsening disease or failing therapy at 4 weeks then a trial of steroids can be considered.

Subjects will return on weeks 1, 2, 4, 8, 12, 16, 20, and 24 while on treatment for their injections, and for the scheduled safety and disease response assessments. Subjects will be allowed to self-administer their injections at home. The full treatment period is 24 doses given weekly for 24 weeks. Subjects who are not able to be tapered off corticosteroids or who require reinstitution of corticosteroid therapy at any time during the study will be counted as treatment failures but may continue on study. Should the IgG4-RD responder index fail to improve by 8 weeks or who develop new organ involvement by week 4 will be deemed a treatment failure, patient's will be deemed treatment failure and can begin corticosteroid or alternative immunosuppressive therapy at the Investigator's discretion. Those who require rituximab or who require addition of other oral immunosuppressive will be counted as treatment failures and will terminate the study.

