All subjects completing the treatment period will have follow up visits off protocolized treatment at 28 and 36 weeks. All AE(s) (including serious AEs and deaths) and use of concomitant medication information will be collected throughout the study from screening through study termination. Subjects developing treatment-emergent AEs or clinically significant safety lab abnormalities will be followed until resolution or until stabilization of the AEs/abnormalities.

Signs and symptoms of IgG4-RD activity will be measured periodically throughout the study using a modification of the IgG4-RD RI ([Carruthers et al. 2012](#), [Wallace et al. 2016](#)). The IgG4-RD RI is based on the Birmingham Vasculitis Activity Score for Wegener's Granulomatosis ([Stone et al. 2001](#)) utilized for the evaluation and licensure of rituximab in ANCA-associated vasculitis ([Stone et al. 2010](#)). The IgG4-RD RI is an instrument designed to detect change in disease activity and identify improvements and worsening in the same or

different organ systems and has been used in prior clinical trials to monitor IgG4-RD disease activity ([Khosroshahi et al 2010](#), [Carruthers et al 2015](#), [Stone et al 2016](#)).

Assessments will include AE assessment, physical examination, vital signs, clinical laboratory testing (clinical chemistry, hematology, serum immunoglobulins, serum IgG4 subclasses, complements, and urinalysis) and concomitant medications. Additional serologic indicators of response will include immunoglobulin levels, IgG4 subclasses, IgE, Eosinophil levels, C3 and C4 levels.

Additional mechanistic studies will be conducted through the MGH NIH-funded Autoimmunity Center of Excellence for IgG4-RD, which has established translational collaborations between the MGH Clinic and the Ragon Institute of Harvard, MGH, and MIT (the laboratory of [name]).

Briefly, peripheral blood mononuclear cells (PBMCs) and plasma will be isolated and frozen from each subject at weeks 0, 1, 4, 12 and 24 corresponding with clinical blood draws. PBMCs and plasma will be stored in liquid nitrogen for preservation. The following experiments will be carried out in batches of 10 patient time points per experiment:

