 - a. Symptom Severity Index
 - b. Glucocorticoid Toxicity Index
 - c. SF-36 Health Survey
 - d. Patient Global Activity VAS
9. Physician-reported outcomes
 - a. Glucocorticoid Toxicity Index
 - b. Physician global activity VAS
 - c. IgG4-RD RI
10. Study drug administration and teaching
11. Study medication dispense

Visit 3 (week 4)-visit 10 (week 36)

Patients will have visits at Weeks 4, 8, 12, and then every 4 weeks per the schedule of assessments shown in Table 1

1. Brief physical exam including vital signs (Full physical exam at EOS)
2. Assessment of signs and symptoms of IgG4-RD
3. Concomitant Medications review
4. Adverse Events Assessments
5. Assessment of signs and symptoms of IgG4-RD activity
6. Abatacept administration (baseline, w4, w12, w20, w28, w36, w44)
7. Laboratory tests (to be drawn before study product administration). See schedule of events.
 - i. Mechanistic samples will be collected from subject at weeks 0, 1, 4, 12 and 24 studies)
8. Patient-reported outcomes (per schedule of events, table 1)
9. Physician reported outcomes (per schedule of events, table 1)
10. Study medication accountability and dispense

Safety follow up visit (if needed)

During the safety follow up the following procedures will be completed

1. Vital signs and Physical exam
2. Concomitant Medications review

3. Adverse Events Assessments
4. Assessment of signs and symptoms of IgG4-RD

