8.2 Endpoints

Primary Efficacy Endpoint

The primary endpoint is complete remission at 24 weeks. Complete remission is defined as an IgG4-RD Responder Index Score of 0 and a prednisone dose of 0 mg/day and no flare since beginning treatment.

Secondary Efficacy Endpoints

- Disease response at 4, 12, 24, and 36 weeks. Disease response will be defined at 6 months as: 1) improvement of ≥ 1 point in the IgG4-RD RI score over baseline; 2) no glucocorticoid use following the week 4 visit; 3) no disease flares, as assessed by the IgG4-RD RI. Disease flare will be defined as recurrence of disease activity or demonstration of a disease exacerbation such that additional therapy beyond the trial protocol is indicated. Such additional therapy may include glucocorticoids or alternative immunosuppressive agents.
- Complete remission at 36 weeks.
- Time to disease remission (IgG4-RD RI = 0)
- Remission rates

- Number of disease flares per subject over time
- Cumulative corticosteroid doses and Glucocorticoid Toxicity Index
- Physician Global Assessment (PGA). A PGA consisting of a 10-centimeter visual analog scale is collected at each patient visit. Only active disease (as opposed to damage) is considered in the scoring of the PGA.
- Symptom Severity Index
- Serum immunoglobulin levels, IgG4 subclass concentrations, IgE levels, eosinophils, and serum C3 and C4

Safety Endpoints

Safety analyses will be performed using all treated subjects.

- The number and percent of subjects experiencing a treatment-emergent adverse event will be tabulated for each coded MedDRA system-organ class and preferred term. Treatment-emergent adverse events will also be tabulated according to intensity and causality.
- All SAEs, discontinuations due to AE, or deaths occurring during the course of the trial will be presented in subject listings.
- The number and percent of subjects experiencing a glucocorticoid-related AE will be tabulated for each coded MedDRA system-organ class and preferred term. Treatment-emergent adverse events will also be tabulated according to intensity and causality.

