

WMA Declaration of Helsinki (18th WMA General Assembly 1964), revised at 59th World Medical Association General Assembly Seoul, October 2008.

17 **APPENDICES**

Efficacy Assessments

A. IgG4-RD Responder Index (IgG4-RD RI)

The IgG4-RD RI is a tool designed to detect change in disease activity and identify improvements and worsening in the same or different organ systems (modified after Carruthers, 2012).

At each assessment, the physician enters a 0-3 score after the organ/site listed with;

0 = Normal or resolved

1 = Improved but still present

2 = New or recurrent disease activity while subject is off treatment, or unchanged from previous visit*

3 = Worsened or new disease manifestation despite treatment

*Unchanged from previous visit will often refer to disease manifestations that require follow-up imaging to assess accurately.

The second column is used to record symptomatic disease; yes=Y, no=N.

The third column records whether there is urgent disease in that site; yes=Y, no=N.

Damage in the organ/site is recorded in the fourth column; yes=Y, no=N.

The fifth column records whether damage in the organ/site is symptomatic; yes=Y, no=N.

Physician Global Assessment of disease activity is denoted on a 100 mm line as covered below.

IgG4-RD Responder Index (Version 25 July 2016)

Scoring Rules

Scoring refers to manifestations of disease activity present in the last 28 days

- Scoring: 0 Normal or resolved
 1 Improved but still present
 2 New / Recurrence while patient is off treatment or unchanged from previous visit*

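### The schedule leaves the IgG4-RD RI and physician VAS unmarked at the week-28 off-drug visit, so weeks 24 to 32 lie outside any scheduled RI window for subjects who complete treatment.

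*Protocol*

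**What the plan says.** Off-drug follow-up is described in section 5: "Subjects will be followed on study for 12 weeks following the last dose for a total study period of up to 36 weeks". Two visits fall in it: "All subjects completing the treatment period will have follow up visits off protocolized treatment at 28 and 36 weeks".

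The second part of the schedule table in section 5.1 has columns for weeks 16 to 24, 28 and 36. The RI row there reads "IgG4-RD RI X X X X" and the VAS row reads "Physician Global Activity VAS X X X X". Set against the columns, both are marked at weeks 16, 20, 24 and 36 and empty at week 28.

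The scoring rules in Appendix A limit the index to four weeks: "Scoring refers to manifestations of disease activity present in the last 28 days". Section 7.2 gives the same window.

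Other parts of the protocol point the other way on week 28. Section 8.2 and the synopsis state of the PGA: "A PGA consisting of a 10-centimeter visual analog scale is collected at each patient visit". Section 5.2, under visits 3 (week 4) to 10 (week 36), lists an assessment of the signs and symptoms of disease activity, and section 5 says that these are measured with the modified RI. The same part of 5.2, however, refers physician-reported outcomes back to the schedule table.

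Three week-36 quantities involve flares. Disease response requires "no disease flares, as assessed by the IgG4-RD RI". Complete remission requires that no flare has occurred since treatment began. The number of flares per subject over time is a secondary endpoint.

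**The concern.** On treatment, RI scoring every four weeks matches the 28-day look-back exactly. The match ends when abatacept stops, although section 7.1 frames efficacy as the ability to sustain improvement and names the RI as the primary efficacy variable. The investigator sees and examines the subject at week 28, yet the table asks for no RI and no physician VAS. Disease response names the RI as the instrument for judging flares, and for most of the off-drug period a site that follows the table would have no RI.

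A score not taken at week 28 cannot be restored by a later analysis plan. Sites may also differ in practice, because one part of the protocol tells them to collect the PGA at every visit and the table tells them not to.

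**Working it through.** **Is the blank real?** The second table has 11 week columns: nine for weeks 16 to 24, then 28 and 36. The RI and VAS rows carry marks in columns 1, 5, 9 and 11, that is weeks 16, 20, 24 and 36. The adverse-event row carries marks in columns 1, 5, 9, 10 and 11, that is weeks 16, 20, 24, 28 and 36. Neighbouring rows therefore place a week-28 mark correctly, and the empty RI and VAS cells are not an effect of text extraction.

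**Inputs**
- RI visits: weeks 0, 1, 4, 8 and 12 (first table) and 16, 20, 24 and 36 (second table), section 5.1.
- Look-back: 28 days = 4 weeks, Appendix A and section 7.2.
- Off-drug period: week 24 to week 36, section 5, so 36 − 24 = 12 weeks.

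**Coverage.** A score at week t covers t − 4 to t.

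| RI visit (week) | Weeks covered |
|---|---|
| 4 | 0–4 |
| 8 | 4–8 |
| 12 | 8–12 |
| 16 | 12–16 |
| 20 | 16–20 |
| 24 | 20–24 |
| 36 | 32–36 |

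Weeks 0 to 24 are covered without a gap. The only uncovered stretch is weeks 24 to 32: 32 − 24 = 8 weeks, and 8/12 = 67% of the off-drug period.

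**With an RI at week 28.** Weeks 24 to 28 become covered. The remainder is weeks 28 to 32: 4 weeks, and 4/12 = 33%. Only a further score at week 32, or a longer look-back at week 36, would bring this to zero.

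**Table against text at week 28**

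| Item | Schedule table, 5.1 | Text |
|---|---|---|
| Physician VAS/PGA | blank | every visit (synopsis, 8.2): direct contradiction |
| RI | blank | activity assessed at visits 3–10 (5.2), measured with the RI (5); but 5.2 sends physician-reported outcomes to the table: ambiguous |

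**What the remaining data can show.** Activity that begins after week 24 has three possible courses:
1. It is treated. The therapy appears in concomitant medication at week 28 or 36.
2. It is untreated and persists into weeks 32 to 36. It falls in the week-36 RI window.
3. It is untreated and resolves before week 32. No scheduled RI covers it; only history, examination or adverse-event reporting could show it.

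Only the third course is exposed to the gap.

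**The case against.** The strongest objection concerns the definition of a flare. Section 8.2 ties it to activity for which therapy beyond the protocol is indicated and sets no RI threshold. Activity that is never treated and settles off drug will often not be a flare at all. The no-flare part of complete remission is not tied to the RI; that link appears only in disease response. This stands, and it narrows the harm considerably. What survives is activity for which therapy was indicated but not given, and flares judged by the RI for week-36 response.

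Four stronger readings are tempting, and the protocol does not support them.
- A reader might infer that nothing is known about disease in weeks 24 to 32. Week 28 has history, an abbreviated examination directed at IgG4-RD symptoms, adverse events and concomitant medication, and the text can be read as asking for both the PGA and an RI-based assessment.
- A reader might infer that flare counts are shown to be too low and remission too high. Any miss would act in that direction, but the protocol gives no basis for saying that one is likely. The RI = 0 part of week-36 remission is measured directly at week 36.
- A reader might infer that the primary endpoint is affected. Sections 4.1 and 8.2 place it at week 24, before the gap. Only the synopsis places it at week 36.
- A reader might take the absence of a week-32 visit as a contradiction of section 5.2. That sentence, "Patients will have visits at Weeks 4, 8, 12, and then every 4 weeks per the schedule of assessments", defers to the schedule, so this is weak.

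The gap also concerns completers only. Under section 5.6, subjects who withdraw early have the end-of-study assessments, which include the RI, four weeks after their last injection.

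**Conclusion.** The point holds as a limited gap in the schedule combined with an internal inconsistency. For subjects who complete treatment, weeks 24 to 32 (8 of 12 off-drug weeks, 67%) are the only part of the study outside a scheduled RI window. The blank VAS cell contradicts section 8.2 and the synopsis, and the blank RI cell fits poorly with section 5.2 read with section 5.

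The result rests on three assumptions: sites follow the table, the 28-day look-back is applied as written, and the off-drug period is counted from week 24 as the protocol does.

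The exposure is confined to activity that begins after week 24, is untreated and resolves before week 32. It bears on RI-assessed flares in week-36 disease response, on flares per subject over time, and on the no-flare condition of week-36 complete remission. With about 10 subjects, one misclassified subject would move a week-36 proportion by 1/10 = 10 percentage points. That is the size of a single miss, not an estimate that one will occur. This is a cheap improvement, not a threat to the trial's main conclusion.

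**What to change.** Mark the IgG4-RD RI and the physician VAS at week 28 in the section 5.1 table. Reconcile that table with section 5.2 (activity assessment at visits 3 to 10) and with the PGA statement in section 8.2 and the synopsis. This reduces the uncovered stretch to weeks 28 to 32, 4 of 12 weeks; it does not remove it.

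Optionally, have the week-36 form record any disease activity since week 28, with its date. Such activity should count as a flare only if it meets the existing section 8.2 definition. Counting any organ activity in that interval as a recurrence would change the definition of flare for the follow-up period alone, and would count disease that had never resolved as a recurrence.

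The cost is two short forms at a visit that already includes an examination, the optional item at week 36, and text edits. No visit or test is added. Week-36 figures may come out slightly less favourable.

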5.2 Study Assessments

Screening Visit

The following procedures will be performed:

1. Obtain written informed consent after consent presentation
2. Obtain Medical history
 - a) Including demographics
 - b) Including history of IgG4-RD
3. Physical examination
4. Record concomitant medication
5. Vital signs including; BP, P, R, T, weight, and height.
 - a. Weight will be measured with outerwear and shoes removed
 - b. Height will be measured with shoes removed (screening visit only)
 - c. Blood pressure and pulse rate obtained after the subject has been supine ≥ 5 minutes
6. Adverse Event monitoring (from time of study drug administration)
7. Laboratory tests:
 - a. CBC with cell differential and platelets
 - b. Chemistry panel
 - c. Urinalysis and urine protein/creatinine ratio
 - d. Urine pregnancy test (only for woman of child bearing age)
 - e. Hepatitis B and C tests (not required if collected 30 days prior to screening visit)
 - f. Serum Immunoglobulin levels (IgM, IgE, IgG)
 - g. Serum IgG4 subclasses
 - h. Complement levels
 - i. Fasting lipid profile
 - j. Mechanistic samples will be collected from subject at weeks 0, 1, 4, 12 and 24 studies)
8. Imaging tests: CT chest, abdomen, pelvis
9. Physician reported outcomes
 - a. IgG4 Responder Index (IgG4-RD RI)
 - b. Physician Global Activity VAS
10. Patient reported outcomes
 - a. Symptom Severity Index
 - b. Glucocorticoid Toxicity Index
 - c. SF-36 Health Survey
 - d. Patient Global Activity VAS

Baseline Visit: Visit 2 (week 1)

The screening (visit 1) and baseline visit (visit 2) could potentially be combined and completed on the same day

The following procedures will be performed:

1. Verify eligibility criteria.
2. Review general medical and IgG4 history
3. Brief physical examination
4. Record concomitant medication
5. Vital signs including; BP, P, R, T, weight, and height.

- a. Weight will be measured with outerwear and shoes removed
- b. Blood pressure and pulse rate obtained after the subject has been supine ≥ 5 minutes
6. Adverse Event monitoring
7. Laboratory tests:
 - a. CBC with cell differential and platelets
 - b. Chemistry panel
 - c. Urinalysis and urine protein/creatinine ratio
 - d. Urine pregnancy test (only for woman of child bearing age)
 - e. Serum Immunoglobulin levels (IgM, IgE, IgG)
 - f. Serum IgG4 subclasses
 - g. Fasting lipid profile
 - h. Mechanistic samples will be collected from subject at weeks 0, 1, 4, 12 and 24 studies)
8. Patient-reported outcomes:
 - a. Symptom Severity Index
 - b. Glucocorticoid Toxicity Index
 - c. SF-36 Health Survey
 - d. Patient Global Activity VAS
9. Physician-reported outcomes
 - a. Glucocorticoid Toxicity Index
 - b. Physician global activity VAS
 - c. IgG4-RD RI
10. Study drug administration and teaching
11. Study medication dispense

Visit 3 (week 4)-visit 10 (week 36)

Patients will have visits at Weeks 4, 8, 12, and then every 4 weeks per the schedule of assessments shown in Table 1

1. Brief physical exam including vital signs (Full physical exam at EOS)
2. Assessment of signs and symptoms of IgG4-RD
3. Concomitant Medications review
4. Adverse Events Assessments
5. Assessment of signs and symptoms of IgG4-RD activity
6. Abatacept administration (baseline, w4, w12, w20, w28, w36, w44)
7. Laboratory tests (to be drawn before study product administration). See schedule of events.
 - i. Mechanistic samples will be collected from subject at weeks 0, 1, 4, 12 and 24 studies)
8. Patient-reported outcomes (per schedule of events, table 1)
9. Physician reported outcomes (per schedule of events, table 1)
10. Study medication accountability and dispense

Safety follow up visit (if needed)

During the safety follow up the following procedures will be completed

1. Vital signs and Physical exam
2. Concomitant Medications review

3. Adverse Events Assessments
4. Assessment of signs and symptoms of IgG4-RD

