1. Flow cytometric quantification of plasmablasts, activated B cells, terminally differentiated CD4+ cytotoxic T cells (CD4+CTLs), terminally differentiated CD8+ cytotoxic T cells (CD8+CTLs), activated follicular helper T (TFH) cells and peripheral helper T (TPH) cells. Terminal differentiation will be defined by the loss of CD28 surface expression and gain of CD57 surface expression within the respective effector (CD45RA-CCR7-) T cell population. These cell populations will be assessed at weeks 0, 1, 4, 12 and 24 to determine the treatment effect on the absolute numbers and proportions of these cell types.
2. Quantified cell populations will be analyzed for correlation with one another, disease activity, plasma IgG4 levels and clinical responsiveness to abatacept.
3. From 5 of the enrolled subjects with known expansions of the respective cell type and clinical responsiveness to abatacept, terminally differentiated CD4+CTLs, terminally differentiated CD8+CTLs and activated B cells will be sorted by FACS at weeks 0, 12 and 24. RNA will be isolated to undergo RT-PCR amplification of the TCR- β /IgH, respectively. Next-Generation Sequencing will be used to define the diversity of the TCR/BCR repertoire longitudinally to ascertain how abatacept may impact clonality.

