6.3 Treatment Protocol

- **Abatacept (Orencia)**: One 125 mg/mL single-dose prefilled glass syringe will be administered by subcutaneous (SC) injection weekly by the patients or caregivers. Patients and caregivers will be trained on how to administer the medication by the study investigators or a designated study staff member during baseline and week 1 visits. Abatacept interruptions or withdrawals will be as per the current U.S. product insert (See Attached Package Insert).

- **Prednisone taper**: Subjects who are on prednisone at baseline will begin an investigator-directed corticosteroid taper designed to discontinue prednisone not later than 8 weeks after the baseline visit.

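### The week-1 mechanistic sample is scheduled at the first-dose visit; read that way, it is a second baseline and the one-week on-treatment cell measurement is lost

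*Protocol*

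**What the plan says.** Section 5 (mechanistic studies) states that blood cells and plasma are to be "isolated and frozen from each subject at weeks 0, 1, 4, 12 and 24 corresponding with clinical blood draws", and gives the purpose: "These cell populations will be assessed at weeks 0, 1, 4, 12 and 24 to determine the treatment effect on the absolute numbers and proportions". Week 1 is therefore one of the points used to judge treatment effect.

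Two places assign these samples to visits.

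- **5.1 Schedule of Assessments.** Week 0 is screening and carries no study drug. Study drug and injection teaching first appear at week 1. Mechanistic samples are marked at weeks 0, 1, 4, 12 and 24. No laboratory test is marked at weeks 2 or 3. Footnote 1 lets screening and the treatment week 1 visit fall on one day.
- **5.2 Study Assessments.** The visit is titled "Baseline Visit: Visit 2 (week 1"). It includes a mechanistic sample (item 7h) and "Study drug administration and teaching" (item 10). It also says: "The screening (visit 1) and baseline visit (visit 2) could potentially be combined and completed on the same day". The next visit block is "Visit 3 (week 4)-visit 10 (week 36").

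Other sections describe week 1 differently. After the sentence on the initial dose, Section 5 says "Subjects will return on weeks 1, 2, 4, 8, 12, 16, 20, and 24 while on treatment"; the synopsis (Study Procedures) has the same list. Section 6.3 places injection training "during baseline and week 1 visits", as two occasions. Section 3.3 gives 25 doses, whereas the synopsis and Section 5 give 24.

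**The concern.** A sample can inform on early treatment effect only if drug has been on board for some time. If week 1 is the day of the first injection, the sample labelled week 1 describes the patient at the start of treatment, not after a week of it. Anyone analysing by nominal week could take it for an on-treatment value.

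Section 5.3 describes the trial as focused on proof of concept and mechanism, without a control group. Within-subject change over time is therefore the only mechanistic evidence available. Section 6.3 also starts the prednisone taper at baseline for subjects who are on prednisone. By week 4 drug effect and steroid withdrawal overlap more than they would at one week. A one-week sample that was never drawn cannot be recovered at the analysis stage.

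**Working it through.** **Inputs.** The 5.1 table has 15 study-drug marks at weeks 1 to 15 and 9 at weeks 16 to 24. Sampling weeks are 0, 1, 4, 12 and 24 (Section 5). The stated course is 24 weekly doses, with 12 weeks from last dose to week 36 (Section 5). About 10 subjects are planned.

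**Step 1: reproduce the stated dose count.** 15 + 9 = 24 marks, which matches the stated 24 doses.

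**Step 2: locate the first dose.** Let f be the schedule week of the first dose. The 24th dose falls at week f + 23, and follow-up to week 36 is 36 − (f + 23) = 13 − f weeks.

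- f = 1: 24th dose at week 24, follow-up 12 weeks. Both match the table and Section 5.
- f = 0: 24th dose at week 23, follow-up 13 weeks. Dosing through week 24 would instead make 25 doses, the figure in Section 3.3.

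The 5.1 table, 5.2, the 24 doses and the 12-week follow-up are therefore mutually consistent only with the first dose at schedule week 1.

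**Step 3: place the samples.** Days since first dose = (s − f) × 7, where s is the sampling week. Doses received before a pre-injection draw = s − f, with a minimum of 0.

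| Sample | f = 1: days, prior doses | f = 0: days, prior doses |
|---|---|---|
| Week 0 | −7 (or 0 if combined), 0 | 0, 0 |
| Week 1 | 0, 0 | 7, 1 |
| Week 4 | 21, 3 | 28, 4 |
| Week 12 | 77, 11 | 84, 12 |
| Week 24 | 161, 23 | 168, 24 |

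With f = 1 the first on-treatment sample is week 4, at day 21 after three doses. The one-week sample (day 7, one dose) exists only in the f = 0 column, which corresponds to the wording of the synopsis, Section 5 and 6.3.

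**Step 4: size.** Planned samples: 5 × 10 = 50. Samples whose role changes: 1 × 10 = 10, or one point in five.

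**Step 5: knock-on effects.** With f = 1, schedule week 24 is 24 − 1 = 23 weeks after the first dose. The 6.3 taper limit of 8 weeks after the baseline visit falls at schedule week 1 + 8 = 9, whereas the synopsis (Study Procedures) sets completion by week 8 and Section 5 by week 4.

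**The case against.** The strongest reply is that the protocol contradicts itself rather than fixing a bad design. The synopsis, Section 5 and 6.3 all point to a week-1 visit distinct from baseline, and a site working from those sections could draw the sample a week after the first dose. That stands: it would be too strong to say that the early measurement does not exist anywhere in the plan. It is missing from 5.1 and 5.2, the sections that tell staff when to draw it.

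Four further points also stand.

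- Pre-dose status at the baseline visit is not stated. It can only be inferred from the laboratory tests being listed before the drug. List order is weak evidence: for the later visits 5.2 lists abatacept before laboratory tests, yet requires the blood to be taken first. Even so, a draw after the injection on the same day would not be a one-week sample.
- A reader might count two of the five points (40%) as wasted. Week 0 is pre-treatment on any reading, so only one point changes role.
- A reader might infer that the analysis will wrongly show no early effect. The protocol names no week-1 contrast, so that is a risk if the sample is treated as on-treatment, not a stated consequence.
- The repertoire sequencing uses weeks 0, 12 and 24 and loses no time point. A second baseline also has some value as a measure of within-subject variation.

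Footnote 3 of 5.1 lists weight at 1, 2, 4, 8 and so on, which appears to follow the week scale and suggests a week-2 contact. The table marks no assessment or draw at that week, so this does not supply the missing sample. The table's visit-number row is garbled in the text as extracted, and nothing here rests on it.

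**Conclusion.** The concern holds as an internal contradiction with a practical cost. Followed as written, 5.1 and 5.2 make one of five mechanistic points a second baseline, or a same-day duplicate of week 0 for subjects whose visits are combined. This affects up to 10 of about 50 planned samples. How many subjects would have combined visits is not given. The earliest on-treatment cell measurement then moves from day 7 to day 21.

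The effect is confined to the exploratory cell objectives. Weeks 4, 12 and 24 remain on treatment, and the primary endpoint does not use these samples. The conclusion assumes that sites draw blood according to 5.1 and 5.2, that every planned sample is obtained, and that 10 subjects are enrolled.

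A reader might also infer that calling the first dose week 0 throughout would settle the matter. The documents do not support that as a simple relabelling. It would place the 24th dose at week 23 with 13 weeks of follow-up, or make 25 doses if dosing runs through week 24. Which calendar is intended is for the sponsor to state.

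**What to change.** - Keep one pre-dose mechanistic sample, at screening or baseline, and state explicitly that it precedes the first injection.
- Move the existing week-1 draw to the return visit one week after the first dose, before that day's injection. On the current table numbering this is schedule week 2, a return that the synopsis and Section 5 already list.
- Label every mechanistic sample by days since first dose, so that the analysis does not depend on which week numbering a site followed.
- Reconcile the synopsis, 3.3, Section 5, 5.1, 5.2 and 6.3 on which visit week 1 means, the week of the first dose, the dose count and the taper deadline. This point does not choose the dosing calendar or the taper rule.

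**Cost.** The number of draws is unchanged. The 5.1 table and 5.2 must carry a draw at that return visit, so subjects must attend in person that week and not only inject at home. The second baseline value is given up.
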